6.0 Study Drug Duration and Compliance

6.1 Study Drug Duration

Induction Period 1

For the safety population SA2, duration of exposure to study drug will be summarized for each treatment group in Induction Period 1.

Duration of exposure in Induction Period 1:

- If the subjects enrolled into Study M16-066 after the Induction Period 1:
 - Duration of exposure = min (the first study drug dose date in Study M16-066 – the first study drug dose date in Induction Period 1, the last study drug dose date in the Induction Period 1 – the first study drug dose date in the Induction Period 1 + 28 days),
- If the subject enrolled into Induction Period 2 after Induction Period 1:
 - Duration of exposure = min (the first study drug dose date in the Induction Period 2 – the first study drug dose date in Induction Period 1, the last study drug dose date in Induction Period 1 – the first study drug dose date in Induction Period 1 + 28 days),
- Otherwise:
 - Duration of exposure = the last study drug dose date in Induction Period 1 – the first study drug dose date in Induction Period 1 + 28 days.

For each treatment group and total in Induction Period 1, the duration of exposure will be summarized by the number of subjects treated, as well as the mean, standard deviation, median, minimum and maximum values. In addition, the number and percentage of subjects exposed to study drug will be summarized for the following exclusive duration intervals:

- 1 – 28 days
- 29 – 56 days
- 57 – 84 days

- 85 – 112 days
- > 112 days

Induction Period 2

For the safety population SA2_P2, the duration of exposure to study drug will be summarized for each treatment group in Induction Period 2.

Duration of exposure in Induction Period 2:

- If the subjects enrolled into Study M16-066 after Induction Period 2:
 - Duration of exposure = min (the first study drug dose date in Study M16-066 – the first study drug dose date in Induction Period 2, the last study drug dose date in Induction Period 2 – the first study drug dose date in Induction Period 2 + 28 days [for IV dose] or 56 days [for SC dose]),
- Otherwise:
 - Duration of exposure = the last study drug dose date in Induction Period 2 – the first study drug dose date in Induction Period 2 + 28 days [for IV dose] or 56 days [for SC dose].

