10.2 Adverse Events

Adverse events (AEs) will be summarized and presented using primary MedDRA System Organ Classes (SOCs) and preferred terms (PTs) according to the version of the MedDRA coding dictionary used for the study at the time of database lock. The actual version of the MedDRA coding dictionary used will be noted in the AE tables and in the clinical study report. Specific adverse events will be counted once for each subject for calculating percentages, unless stated otherwise. In addition, if the same adverse event occurs multiple times within a subject, the highest severity and level of relationship to investigational product will be reported.

Summaries of AEs discussed in this section will be provided for SA2 and SA2_P2 population. For SA2_ALL population, exposure-adjusted AEs per 100 patient-years will be provided as described in Section 10.2.4. For exposure-adjusted event rate (EAER) calculation, the numerator will be the total number of AEs reported for the event (i.e., a subject can contribute more than one event to the numerator) and the denominator will be the total exposure time among subjects under the treatment group. The number of AEs reported (numerator), the total number of years of study drug exposure (denominator, calculated as total number of days exposed to study drug (i.e., last dose date – first dose date + 140 days) for all treated subjects divided by 365.25), and the exposure-adjusted AE event rate per 100 patient-years calculated as ([numerator (number of AEs)/denominator]) × 100 will be presented for each treatment group.

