10.2.1 Treatment-Emergent Adverse Events

The Treatment-Emergent Adverse Events (TEAEs) for SA2, SA2_P2 and the SA2_ALL populations are defined as follows:

Induction Period 1 (SA2 population):

TEAEs for Induction Period 1 are defined as events that begin either on or after the first dose of the study drug in Induction Period 1 and

- before first dose of study drug in Induction Period 2 if the subject is enrolled into Induction Period 2 or
- before first dose of study drug in the Maintenance Study (M16-066) if the subject is enrolled into the Maintenance Study (M16-066) or
- within 140 days after the last dose administration of the study drug for subjects who are not enrolled in Induction Period 2 and do not participate in the Maintenance Study (M16-066); or for subjects who are responders in Induction Period 1 but do not participate in the Maintenance Study (M16-066).

Induction Period 2 (SA2_P2 population):

TEAEs for Induction Period 2 are defined as events that begin either on or after the first dose of risankizumab in Induction Period 2 and

- before first dose of study drug in the Maintenance Study if the subject is enrolled into the Maintenance Study (M16-066) or
- within 140 days after the last dose administration of the study drug for subjects who do not participate in the Maintenance Study (M16-066).

SA2_ALL population:

TEAEs are defined as events that begin either on or after the first dose of risankizumab in either Induction Period 1 or Induction Period 2 and

- before first dose of study drug in the Maintenance Study (M16-066) if the subject is enrolled into the Maintenance Study (M16-066) or
- within 140 days after the last dose of risankizumab in this study for subjects who do not participate in the Maintenance Study (M16-066).

Events where the onset date is the same as the study drug start date are assumed to be treatment-emergent, unless the study drug start time and the adverse event start time are collected and the adverse event start time is prior to the study drug start time. If an incomplete onset date was collected for an adverse event, the event will be assumed to be treatment-emergent unless there is other evidence that confirms that the event was not treatment-emergent (e.g., the event end date was prior to the study drug start date).

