10.2.2 Adverse Event Overview

For SA2 and SA2_P2 populations, an overview of AEs will be presented consisting of the number and percentage of subjects experiencing at least one event for each of the following AE categories:

- Any TEAE
- Any COVID-19 related TEAE
- Any TEAE related to study drug according to the investigator
- Any severe TEAE
- Any serious TEAE
- Any TEAE leading to discontinuation of study drug
- Any TEAE leading to death
- TEAE of Safety Interest (as defined in)

- All deaths
 - COVID-19 related deaths
 - Deaths occurring \leq 140 days after last dose of study drug
 - Deaths occurring $>$ 140 days after last dose of study drug.

Additional AEs may be considered for tabulation/summary based on recommendations from Clinical and Safety as deemed appropriate.

The point estimate and 95% CI (using normal approximation and separate group variance) will also be provided for the treatment difference in AE percentage between risankizumab group and the placebo group for analyses performed on SA2 population.

For SA2 and SA2_P2 populations, an overview of the ASI will be provided similarly and the categories of ASI are defined in [Appendix B](#).

In addition, for SA2 and SA2_P2 populations, an overview of AEs per 100 patient-years of study exposure and an overview of ASI per 100 patient-years of study exposure will be presented. The number of TEAEs reported, the total number of years of study drug exposure, and the TEAE rate per 100 patient-years will be presented. The point estimate and 95% CI will be provided for the treatment difference between risankizumab group and the placebo group.

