10.2.4 Treatment-Emergent Adverse Events per Patient-Years of Exposure

For SA2 and SA2_P2 populations, an overview of AEs per 100 patient-years of study exposure and an overview of ASI per 100 patient-years of study exposure will be presented.

Exposure-adjusted AEs per 100 patient-years will be provided for SA2_ALL for the following categories:

- AE overview
- ASI overview
- All TEAEs by SOC and PT
- All serious TEAEs by SOC and PT
- All Severe TEAEs by SOC and PT
- TEAEs related to study drug according to the investigator by SOC and PT
- TEAEs leading to discontinuation of study drug by SOC and PT
- TEAE leading to death by SOC and PT
- COVID-19 related TEAE by SOC and PT

- TEAE by PT and sorted by decreasing frequency for the total active group
- SAEs (including deaths) and AEs leading to study drug discontinuation by SOC and PT and in listing format.
- ASI by SOC and PT (or by Adjudicated Terms)

Calculation of EAER is defined in Section 10.2.

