10.2.5 SAEs (Including Deaths) and Adverse Events Leading to Study Drug Discontinuation

SAEs (including deaths) and AEs leading to study drug discontinuation will be summarized by SOC and PT and in listing format. Calculation of EAER is defined in Section 10.2.

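### SAP 10.2 counts adverse events only up to rollover but divides by patient-years running to last dose plus 140 days, so exposure-adjusted rates come out too low

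*SAP*

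**What the plan says.** SAP 10.2.2 and 10.2.4 plan overviews of adverse events and of areas of safety interest per 100 patient-years for SA2 (Period 1) and SA2_P2 (Period 2). In 10.2.2 the plan adds: "The point estimate and 95% CI will be provided for the treatment difference between risankizumab group and the placebo group". SAP 10.2.4 plans further exposure-adjusted tables for SA2_ALL and closes with "Calculation of EAER is defined in Section 10.2". SAP 10.2.5 makes the same reference.

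In SAP 10.2 the numerator is the number of events. The denominator is last dose date minus "first dose date + 140 days) for all treated subjects divided by 365.25".

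SAP 10.2.1 sets the event window. In SA2, counting stops "before first dose of study drug in Induction Period 2 if the subject is enrolled into Induction Period 2", or before the first M16-066 dose for subjects who go there. Otherwise it runs "within 140 days after the last dose administration of the study drug for subjects who are not enrolled in Induction Period 2" and who do not enter M16-066. In SA2_P2 and SA2_ALL it likewise stops at the first M16-066 dose, or at 140 days after the last dose for subjects who do not enter that study.

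Two other places in the SAP do cap time at rollover. SAP 6.1 opens its formula for subjects entering Period 2 with "Duration of exposure = min (the first study drug dose date in the Induction Period 2", the alternative being last dose plus 28 days. SAP 9.4.2 ends time at risk at the first Period 2 or M16-066 dose, but only for UC-related hospitalization.

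**The concern.** A rate per patient-year is meaningful only if the time in the denominator is the time during which an event would have been counted. Here a subject who rolls over keeps adding denominator time after counting has stopped. For a placebo subject entering Period 2, that extra time follows the start of risankizumab 1200 mg IV, yet it is credited to placebo with its events left out.

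Period 1 is the only placebo-controlled part of Sub-Study 2, and these overviews are the planned adjustment for follow-up time. Followed literally, the formula understates the absolute rates and the displayed risk difference.

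**Working it through.** The plan states no adverse event rate or patient-year total, so there is none to reproduce. One stated figure does confirm how the 140 days run. The 45-week maximum duration in SAP 2.2 is 35 days of screening + 140 days to the last dose at Week 20 + 140 days = 315 days = 45.0 weeks, so the 140 days start at the last dose.

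**Inputs**
- Period 1 doses at Weeks 0, 4 and 8 (SAP 2.2): last minus first dose = 56 days.
- Period 2 starts at Week 12, Day 84 (SAP 2.2).
- First M16-066 dose: no date is given; Day 84 is assumed. The 7-day visit window (Protocol Appendix C) gives Day 77 to 91.
- Share not rolling over, q: not documented, so shown as a range.
- Event rate: assumed constant over time.

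**Step 1: one subject, three doses, rolls over.** Denominator = 56 + 140 = 196 days. Counted time = 84 days. Shown/true rate = 84/196 = 0.43 (77/196 = 0.39 to 91/196 = 0.46). The excess is 196 − 84 = 112 days.

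**Step 2: an SA2 arm.** Non-rollers with three doses are counted for 196 days, so counted time per subject is 84(1 − q) + 196q. The 10.2 denominator is 196 days; the SAP 6.1 duration is 84 days.

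| Rollover share | Counted days | Shown/true, 10.2 | Shown/true, 6.1 |
|---|---|---|---|
| 100% | 84.0 | 0.43 | 1.00 |
| 95% | 89.6 | 0.46 | 1.07 |
| 90% | 95.2 | 0.49 | 1.13 |
| 80% | 106.4 | 0.54 | 1.27 |

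**Step 3: why SAP 6.1 is not a substitute.** It fits a subject who rolls over on time (84/84 = 1.00) and nearly fits one who rolls over on Day 91 (91/84 = 1.08). For a non-roller, the event window exceeds the 6.1 duration by 196/84 = 2.3 times after three doses, 168/56 = 3.0 after two and 140/28 = 5.0 after one.

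**Step 4: the other populations, for subjects who enter M16-066.**
- SA2_P2, entering near Day 168: 84/196 = 0.43.
- SA2_ALL, risankizumab responder entering after Period 1: 84/196 = 0.43.
- SA2_ALL, risankizumab in both periods, entering near Day 168: 168/(140 + 140) = 0.60.

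**Step 5: effect on the planned difference.** Take assumed true rates of 300 and 260 per 100 patient-years, with all subjects rolling over. They are shown as 300 × 84/196 = 129 and 260 × 84/196 = 111, so a difference of 40 appears as 17. With equal rollover, an interval built from the same counts and patient-years shrinks by the same factor.

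**Step 6: after correction.** If the denominator ends with the event window, shown/true is 1.00 at any rollover share. If all 966 subjects roll over at Day 84, patient-years fall from 644 × 196/365.25 = 345.6 to 644 × 84/365.25 = 148.1 on risankizumab, and from 172.8 to 74.1 on placebo.

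**The case against.** The strongest reply is that 10.2 may not govern SA2. Its formula follows directly on a sentence about SA2_ALL, and the cross-reference in 10.2.4 closes the SA2_ALL list. For SA2, 10.2.2 speaks only of years of study drug exposure, and SAP 6.1 defines an exposure duration that is capped at rollover. If everyone rolled over on time, that duration would be exactly right.

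Part of this stands: applying 10.2 to SA2 is an inference. It is still the better reading. SAP 10.2.2 names the same quantity that 10.2 defines, and 10.2 presents its rates by treatment group, whereas SA2_ALL is a single combined group (SAP 10.1). Even on the narrower reading the mismatch remains for SA2_ALL, whose events also stop at the first M16-066 dose.

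The case for SAP 6.1 also has some force. Follow-up after discontinuation is a premature-discontinuation visit and one call at 140 days (Protocol 5.1), so late events may be under-reported. If non-rollers reported nothing beyond 28 days after their last dose, the 6.1 duration would give the true rate. But that relies on incomplete reporting; it does not match the window in which the SAP says events count.

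It is also fair that the consequence is limited. The SA2 percentages, for which a confidence interval "will also be provided for the treatment difference in AE percentage between risankizumab group and the placebo group", do not use this denominator, and no safety hypothesis rests on the rates. A programmer might add the cap unasked, but the SAP writes caps explicitly in 6.1 and 9.4.2, while 10.2 specifies all treated subjects.

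**Conclusion.** Wrong as written, rather than a missing detail: following 10.2 literally gives rates that are too low whenever subjects roll over. For SA2 the rates and rate difference are shown at 43% of true size if all roll over, 46% at 95%, 49% at 90% and 54% at 80%. For SA2_ALL the figure is 43% to 60% among subjects who enter M16-066. These figures assume three doses on schedule, rollover near Day 84 (or Day 168 after Period 2) and a constant event rate. Efficacy analyses and type I error control are unaffected.

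Three stronger conclusions are tempting but are not supported:
- A reader might infer that the rates are always less than half their true size. With three doses, [84(1 − q) + 196q]/196 reaches 0.50 at q = 14/112 = 12.5% and exceeds it beyond that; the actual share is not documented.
- A reader might infer that unequal rollover creates a false rate ratio whichever denominator is used. The SAP plans a difference, not a ratio; shares by arm, and so the direction, are unknown; and under SAP 6.1 the effect disappears if non-rollers report nothing after 28 days.
- A reader might extend the criticism to the crude percentages. Their unequal observation time follows from the protocol's own definition of treatment-emergent events (Protocol 8.1.7). Its direction is unknown. An assumed 5% versus 20% non-rollover moves a 45% event by 4.5 points, inside a confidence interval half-width of about 6.7.

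**What to change.** In SAP 10.2, end each subject's patient-time at the end of that subject's own event window under 10.2.1. For SA2 this is the earliest of first Period 2 dose, first M16-066 dose, or last Period 1 dose plus 140 days. For SA2_P2 and SA2_ALL, use the matching window. State that exposure in the rates of 10.2.2, 10.2.4, 10.2.5 and 10.2.6 means this time and not the SAP 6.1 duration. SAP 9.4.2 already has a model for the cap.

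The cost is one sentence and a small programming change, using dates already collected. No design element changes. The downside is that the corrected rate will be somewhat low if late events in non-rollers go unreported. In the extreme case where none are reported beyond 28 days after the last dose, it would be 76% to 96% of true, assuming 3% to 20% non-rollover and one to three doses in non-rollers. For example, with 20% and one dose: (84 × 0.8 + 28 × 0.2)/(84 × 0.8 + 140 × 0.2) = 72.8/95.2 = 0.76.

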10.2.1 Treatment-Emergent Adverse Events

The Treatment-Emergent Adverse Events (TEAEs) for SA2, SA2_P2 and the SA2_ALL populations are defined as follows:

Induction Period 1 (SA2 population):

TEAEs for Induction Period 1 are defined as events that begin either on or after the first dose of the study drug in Induction Period 1 and

- before first dose of study drug in Induction Period 2 if the subject is enrolled into Induction Period 2 or
- before first dose of study drug in the Maintenance Study (M16-066) if the subject is enrolled into the Maintenance Study (M16-066) or
- within 140 days after the last dose administration of the study drug for subjects who are not enrolled in Induction Period 2 and do not participate in the Maintenance Study (M16-066); or for subjects who are responders in Induction Period 1 but do not participate in the Maintenance Study (M16-066).

Induction Period 2 (SA2_P2 population):

TEAEs for Induction Period 2 are defined as events that begin either on or after the first dose of risankizumab in Induction Period 2 and

- before first dose of study drug in the Maintenance Study if the subject is enrolled into the Maintenance Study (M16-066) or
- within 140 days after the last dose administration of the study drug for subjects who do not participate in the Maintenance Study (M16-066).

SA2_ALL population:

TEAEs are defined as events that begin either on or after the first dose of risankizumab in either Induction Period 1 or Induction Period 2 and

- before first dose of study drug in the Maintenance Study (M16-066) if the subject is enrolled into the Maintenance Study (M16-066) or
- within 140 days after the last dose of risankizumab in this study for subjects who do not participate in the Maintenance Study (M16-066).

Events where the onset date is the same as the study drug start date are assumed to be treatment-emergent, unless the study drug start time and the adverse event start time are collected and the adverse event start time is prior to the study drug start time. If an incomplete onset date was collected for an adverse event, the event will be assumed to be treatment-emergent unless there is other evidence that confirms that the event was not treatment-emergent (e.g., the event end date was prior to the study drug start date).

All treatment-emergent AEs will be summarized overall, as well as by primary MedDRA SOC and Preferred Term. The SOCs will be presented in alphabetical order, and the PTs will be presented in alphabetical order within each SOC.

The number and percentage of subjects experiencing treatment-emergent AEs will be summarized.

10.2.2 Adverse Event Overview

For SA2 and SA2_P2 populations, an overview of AEs will be presented consisting of the number and percentage of subjects experiencing at least one event for each of the following AE categories:

- Any TEAE
- Any COVID-19 related TEAE
- Any TEAE related to study drug according to the investigator
- Any severe TEAE
- Any serious TEAE
- Any TEAE leading to discontinuation of study drug
- Any TEAE leading to death
- TEAE of Safety Interest (as defined in)

- All deaths
 - COVID-19 related deaths
 - Deaths occurring \leq 140 days after last dose of study drug
 - Deaths occurring $>$ 140 days after last dose of study drug.

Additional AEs may be considered for tabulation/summary based on recommendations from Clinical and Safety as deemed appropriate.

The point estimate and 95% CI (using normal approximation and separate group variance) will also be provided for the treatment difference in AE percentage between risankizumab group and the placebo group for analyses performed on SA2 population.

For SA2 and SA2_P2 populations, an overview of the ASI will be provided similarly and the categories of ASI are defined in [Appendix B](#).

In addition, for SA2 and SA2_P2 populations, an overview of AEs per 100 patient-years of study exposure and an overview of ASI per 100 patient-years of study exposure will be presented. The number of TEAEs reported, the total number of years of study drug exposure, and the TEAE rate per 100 patient-years will be presented. The point estimate and 95% CI will be provided for the treatment difference between risankizumab group and the placebo group.

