2.2 Study Design Overview

Study M16-067 Sub-Study 2 is a Phase 3, multicenter, randomized, double-blind, placebo-controlled study designed to evaluate the efficacy and safety of risankizumab as

induction therapy in adult subjects with moderately to severely active UC, defined as Adapted Mayo score of 5 – 9 points (using the Mayo scoring system, excluding Physician's Global Assessment) with an endoscopic subscore of 2 or 3 on screening endoscopy, confirmed by central review.

Sub-Study 2 will enroll subjects who have had an intolerance or inadequate response (IR) to prior biologic therapy (bio-IR) and subjects who have not had an intolerance or inadequate response to prior biologic therapy (non-bio-IR). The bio-IR enrollment in Sub-Study 2 will be approximately 541 subjects and the non-bio-IR enrollment will be approximately 425 subjects.

The bio-IR population is defined as subjects with documented intolerance or inadequate response to one or more of the approved biologics for UC (infliximab, adalimumab, golimumab, and/or vedolizumab) or tofacitinib. The non-bio-IR population will include subjects who had an inadequate response or intolerance to conventional therapy.

Conventional therapy is defined as one or more of the following: aminosalicylates, oral locally acting steroids (e.g., budesonide, beclomethasone), systemic corticosteroids (prednisone or equivalent), or immunomodulators. This population will also include subjects who have received biologic therapy or tofacitinib in the past but stopped therapy based on reasons other than inadequate response or intolerance (e.g., change in reimbursement coverage, well-controlled disease).

The study duration may be up to 45 weeks, including a Screening period of approximately 35 days, a 12-week Induction Period 1, a 12-week Induction Period 2 for those subjects who do not achieve clinical response at Week 12, and a 140-day follow-up period from the last dose of study drug.

[figure not shown]
Sub-Study 2 Induction Period 1:

Subjects (n = 966) who meet all of the inclusion criteria and none of the exclusion criteria will be enrolled into the double-blind 12-week study and randomized in a 2:1 ratio to one of the following treatment groups:

- Group 1: Risankizumab 1200 mg IV Weeks 0, 4, 8 (n = 644)
- Group 2: Placebo IV Weeks 0, 4, 8 (n = 322)

The schematic of the Induction Period 1 is shown in [Figure 1](#).

Figure 1. Study Schematic of Induction Period 1

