9.0 Efficacy Analyses

9.1 General Considerations

All efficacy analyses will be conducted based on ITT2 for Induction Period 1. The overall type I error rate of the primary and secondary endpoints will be strongly controlled using a graphical multiple-testing procedure¹ as described in Section 13.0. Analyses for the efficacy endpoints in Induction Period 2 will be performed based on ITT2_P2.

The primary analysis will be performed after all ongoing subjects have completed the Sub-Study 2 activities up to Week 24 and the Sub-Study 2 database has been locked. This will be the only and final analysis for the primary and secondary efficacy endpoints as well as all additional efficacy endpoints in Sub-Study 2. Treatment assignments will be unblinded to AbbVie for statistical analyses.

Unless otherwise specified, categorical variables will be analyzed using Cochran-Mantel-Haenszel (CMH) test for common risk difference, stratified by Advanced Therapies-IR status (yes vs no), baseline steroid use (yes vs no), and baseline Adapted Mayo score (≤ 7 vs > 7). If there is a stratum for a treatment group that has no subject in it, a value of 0.1 will be added to all cells in the corresponding table in order to prevent dividing by 0, as suggested in Greenland and Robins (1985).³ Greenland and Robins (1985)³ variance estimator is used for the common risk difference. For all stratification factors (including the randomization stratification factors) used for CMH analyses, their values will be based

on actual values. Continuous variables collected longitudinally (more than one post baseline visits) will be analyzed using Mixed-Effect Model Repeat Measurement (MMRM) method. Continuous variables collected with only one post baseline visit will be analyzed using Analysis of Covariance (ANCOVA) model. For multi-level categorical endpoints PGIC, percentage of each outcome category will be reported descriptively, and no statistical comparison will be performed. For time to event analysis, Kaplan-Meier method will be used. For all stratification factors (including the randomization stratification factors) used for analyses, their values will be based on actual values.

Baseline refers to the last non-missing observation on or before the first administration of study drug in Induction Period 1 or randomization if no study drug is given.

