10.2.6 Areas of Safety Interest

Areas of Safety Interest will be summarized by SOC and PT and will be based on standardized or company MedDRA queries (SMQs or CMQs). Adjudicated cardiovascular events will be summarized and presented by treatment group using the CAC adjudicated categories. Areas of Safety Interest are categorized as follows:

- Adjudicated MACE
- Adjudicated extended MACE
- Serious infections
- Active Tuberculosis
- Opportunistic infections excluding tuberculosis and herpes zoster
- Herpes zoster
- Malignancies (Malignant tumours, NMSC and Malignancies excluding NMSC)
- Hypersensitivity
- Serious hypersensitivity
- Adjudicated Anaphylactic reactions
- Hepatic events

- Injection site reactions

Detailed information about the search criteria is provided in [Appendix C](#).

In addition, an overview of ASI per 100 patient-years of study exposure will be presented. The number of TEAEs reported, the total number of years of study drug exposure, and the TEAE rate per 100 patient-years will be presented.

The exposure adjusted incidence rate (censored at the time of first event) may be conducted for deaths and selected Areas of Safety Interest categories including adjudicated cardiovascular events, malignant tumors, non-melanoma skin cancer (NMSC), and malignant tumors excluding NMSC, as appropriate.

Tabular listings of ASI listed above will also be provided.

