Appendix B. Definition of Areas of Safety Interest

Areas of Safety Interest (ASI) will be identified using the following search criteria:

ASI Grouping	Categories (ASI)	Search Criteria	Terms to Display	Include in AE Overview (Y/N)
Adjudicated CV Events	MACE	Adjudicated terms will be identified using CECAT and CETERM from the CE SDTM dataset.	
Display underlined terms defined by the following adjudicated terms:
 
 • CV Death which includes all CETERM values with CEDECOD= "Cardiovascular death" or "Death due to stroke" • Non-fatal Myocardial infarction • Non-fatal Stroke 	Y
	Extended MACE	Adjudicated terms will be identified (for MACE +) using CECAT and CETERM from the CE SDTM dataset.	
Display underlined terms from MACE and underlined terms below:
 
 • Hospitalization for Unstable Angina • Coronary Revascularization Procedures 	Y

ASI Grouping	Categories (ASI)	Search Criteria	Terms to Display	Include in AE Overview (Y/N)
Serious Infections, TB, and Opportunistic Infections (including Herpes Zoster)	Serious Infections	Serious PTs of the SOC Infections and Infestations	PTs	Y
	Active TB	Active Tuberculosis CMQ (code 10000002)	PTs	Y
	Opportunistic Infections Excluding Tuberculosis and Herpes Zoster	Opportunistic infections CMQ excluding Tuberculosis and Herpes Zoster (code 10000105)	PTs	Y
	Herpes Zoster	Herpes zoster CMQ (code 10000079)	PTs	Y
Malignancies	Malignant Tumours	Narrow Malignant tumours (SMQ 20000194)	PTs	Y
	Non-Melanoma Skin Cancer (NMSC)	Broad Skin malignant tumours (SMQ 20000204) excluding terms identified by the Melanoma CMQ (code 10000100)	PTs	Y
	Malignancies excluding NMSC	'Malignancies excluding NMSC' is identified by the 'Malignant Tumours' search excluding terms identified by the 'Non-melanoma skin cancer' (NMSC) search.	PTs	Y
Hypersensitivity Reaction	Hypersensitivity	Narrow Hypersensitivity (SMQ 20000214)	PTs	Y – serious events separately summarized

ASI Grouping	Categories (ASI)	Search Criteria	Terms to Display	Include in AE Overview (Y/N)
Anaphylactic Reaction	Adjudicated Anaphylactic Reaction	Adjudicated terms will be identified using SDTM data (e.g., CE and PR domains).	Adjudicated term defined in the charter	Y

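### SAP 10.2.2 uses a Wald interval for adverse event percentage differences with no sparse-row rule, so at 644/322 it collapses to 0 to 0 at 0 vs 0 and excludes zero at 4 vs 0

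*SAP*

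**What the plan says.** SAP 10.2.2 builds an overview table of the number and percentage of subjects with each category of adverse event. It then adds, for SA2 only: "The point estimate and 95% CI (using normal approximation and separate group variance) will also be provided for the treatment difference in AE percentage". The comparison is of risankizumab with placebo. A normal approximation with separate group variances is the unpooled Wald interval.

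The rows of that table include treatment-emergent events leading to death, all deaths, COVID-19 related deaths, and "TEAE of Safety Interest (as defined in" an appendix. For areas of safety interest (ASIs) the section adds that, for SA2 and SA2_P2, "an overview of the ASI will be provided similarly and the categories of ASI are defined in" SAP Appendix B. The Appendix B column headed "Include in AE Overview (Y/N" is marked Y for MACE, active tuberculosis and adjudicated anaphylactic reaction, among others.

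SAP 10.1 to 10.2.6 contain no minimum count, continuity correction, exact or score alternative, or suppression rule. The 0.1 cell addition in SAP 9.1 does not help. It belongs to the stratified CMH risk difference and is triggered by a stratum without subjects, not by a row without events. Protocol 8.1.7 names Fisher's exact test for each preferred term. Section 10 of the Sub-Study 2 SAP does not repeat it, and it would give a p-value per term, not an interval for an overview row.

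**The concern.** The Wald variance in each arm is built from the observed proportion, so an arm with no events contributes zero variance. If neither arm has an event, the interval has zero width and claims certainty that about 1,000 subjects cannot supply. If only placebo has no events, the interval ignores all uncertainty about the placebo rate and is too short on the harm side. With 2:1 allocation the smaller arm is the one more likely to be empty, so the distortion falls mainly towards apparent harm from risankizumab.

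Deaths, MACE, active tuberculosis and anaphylaxis over a 12-week period are rows where zero or very small counts are plausible. They are also rows a safety reader looks at closely. At stake is whether the printed error bars in those rows mean what they say.

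**Working it through.** **Inputs.** n1 = 644 and n2 = 322, the planned arms in SAP 2.2. SA2 counts treated subjects, so actual denominators may be slightly smaller. Confidence level 95%, z = 1.96, z² = 3.84. The event counts are illustrations and the event rates are assumptions, because the documents give neither. The plan prints no figure for this interval, so there is none to reproduce.

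**Wald interval as specified.** With p1 = a/644, p2 = b/322 and d = p1 - p2, the interval is d ± z·√[p1(1-p1)/n1 + p2(1-p2)/n2].

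- 0 vs 0: both variance terms are 0, so the interval is 0 to 0.
- 3 vs 0: -0.06 to 0.99 percentage points, which includes zero.
- 4 vs 0: p1 = 4/644 = 0.62%. The standard error is √(0.006211 × 0.993789/644) = 0.310 points, and 1.96 × 0.310 = 0.607. The interval is 0.62 ± 0.61, or 0.014 to 1.228, which excludes zero.

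The 4 vs 0 result does not depend on the exact arm size. With no placebo events the lower limit is positive whenever a > 3.84(1-p1), which 4 always satisfies.

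**Fisher benchmark at 4 vs 0.** With four events split about 2:1 by chance, the splits no more probable than 4-0 are 4-0, 1-3 and 0-4. Approximately, (2/3)⁴ + 4(2/3)(1/3)³ + (1/3)⁴ = 0.198 + 0.099 + 0.012 = 0.31. The exact hypergeometric value is 0.308.

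**Newcombe hybrid-score interval.** Take Wilson limits (l, u) in each arm. The lower limit is d - √[(p1-l1)² + (u2-p2)²] and the upper limit is d + √[(u1-p1)² + (p2-l2)²].

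- 0 vs 0: u1 = 3.84/(644 + 3.84) = 0.59% and u2 = 3.84/(322 + 3.84) = 1.18%, so the interval is -1.18 to 0.59.
- 4 vs 0: l1 = 0.24%, u1 = 1.59%. The lower limit is 0.62 - √(0.38² + 1.18²) = -0.62 and the upper is 1.59.
- 8 vs 0: -0.09 to 2.43. 9 vs 0: 0.05 to 2.63, the first exclusion of zero with an empty placebo arm.

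**How often it matters, at assumed equal true rates.** Exact enumeration over both binomials gives the chance that the Wald interval lies wholly above zero (nominal 2.5%), and the share of those exclusions with no placebo event:

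| Rate in both arms | Wald wholly above zero | Share with no placebo event |
|---|---|---|
| 0.1% | 0.3% | nearly all |
| 0.2% | 2.2% | nearly all |
| 0.3% | 5.0% | nearly all |
| 0.5% | 8.1% | 99% |
| 1% | 5.3% | 66% |
| 2% | 4.3% | 3.5% |

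The maximum is 8.1%, near 0.54%. Minimum two-sided coverage at equal rates is 91.0%, at about 0.55%. Over equal rates of 0.05% to 2%, Newcombe lies wholly above zero in at most 1.5% of trials and wholly below in at most 2.9%.

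**Common rows.** At 64 vs 32 (about 10% in each arm) the total width is 8.00 points for Wald and 8.09 for Newcombe. At about 20% it is 10.69 for both.

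**The case against.** **No decision rests on these intervals.** They carry no p-value, threshold or alpha. SAP 10.2.5 says "SAEs (including deaths) and AEs leading to study drug discontinuation will be summarized by SOC and PT and in listing format", and SAP 10.2.6 says "Tabular listings of ASI listed above will also be provided". MACE and anaphylaxis are adjudicated. A reader who sees 4 vs 0 also sees the counts. This stands and limits the severity. It does not make a zero-width 95% interval correct.

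**Over-flagging may suit a safety table.** At assumed true rates of 1% vs 0.1%, Wald lies above zero in 67% of trials and Newcombe in 15%. Preferring sensitivity followed by case review is a fair position. However, part of the 67% comes from the same mechanism that gives 5% to 8% false exclusions when the rates are equal.

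**Application to each ASI row is inferred.** The sentence on the interval covers SA2. The ASI sentence also covers SA2_P2, which has no placebo group, so the ASI overview may have been meant to repeat only counts and percentages. Appendix B makes the wider reading natural, but the SAP does not state it. The death rows do not depend on this reading.

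**Stronger inferences that the documents do not support.**

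- A reader might infer that Wald also misses real differences in the other direction, for example at 0 vs 3, where it gives -1.98 to 0.12 and two-sided Fisher gives p = 0.037. That contrast depends on the Fisher convention: doubling the one-sided tail gives 0.074. It also concerns events on placebo only, so it would not be a missed harm.
- A reader might infer that every excess exclusion comes from an empty placebo row. That is mainly so up to a rate of about 1%, but at 2% only 3.5% of the exclusions have no placebo event.
- A reader might quote coverage near 71% to 72%. Those figures arise only at assumed unequal rates such as 0.1% vs 0.2% or 0.2% vs 0.4%. The documents give no rates that would support them.

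**Conclusion.** The point holds as a narrow one. Applied as written, SAP 10.2.2 gives wrong error bars in sparse rows: 0 to 0 at 0 vs 0, and an interval excluding zero at 4 vs 0 where Fisher's p is 0.31. The excess of apparent harm signals is 5% to 8% against 2.5% at assumed equal rates of 0.3% to 1%, and equal-rate coverage falls no lower than 91.0%. At 0.2% and below there is no excess above 2.5%, but the zero-width interval at 0 vs 0 remains.

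This rests on the planned arm sizes, on assumed event rates, and, for the ASI rows only, on the natural reading of SAP 10.2.2 with Appendix B. A reader might go further and infer a type I error breach or an unreliable safety conclusion. The documents do not support that: the intervals are descriptive, no safety decision is tied to them, and the efficacy inference is untouched. The change is worth considering because it is cheap, not because the trial's conclusions depend on it.

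**What to change.** In SAP 10.2.2, replace the parenthetical naming the interval method with the Newcombe hybrid-score interval for risankizumab-placebo differences in adverse event percentage. State that the same interval applies to the ASI overview differences in SA2. Keep the counts and listings beside it. Settle this before the step in SAP 9.1 at which "Treatment assignments will be unblinded to AbbVie for statistical analyses".

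The cost is one phrase, one software option and fewer harm-side exclusions of zero. With no placebo events, zero is first excluded at 9 vs 0 instead of 4 vs 0. At assumed rates of 1% vs 0.1% the interval lies above zero in 15% of trials instead of 67%, and at 2% vs 0.1% in 78% instead of 94%. The sponsor should accept that loss knowingly and rely on listings and adjudication for single rare events.

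The edit does not reach the last paragraph of SAP 10.2.2, which promises a 95% interval for exposure-adjusted rate differences without naming a method. That interval also meets rows with no events, and its method should be named at the same time.
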